4.2 Discussion of Study Design

Choice of Control Group

This is an open-label study. There is no separate control group.

Appropriateness of Measurements

The primary efficacy measure used in this study (FLSQ) is a validated measure. Allergan has also developed and validated upper facial line severity scales (AGLSS, LCLSS, and FHLSS) in accordance with the United States Food and Drug Administration requirement. All efficacy-related measurements in this study are standard for assessing facial aesthetics correction (for GL, LCL, and FHL). All clinical procedures in this study are standard and generally accepted.

Suitability of Subject Population

The study population will include male and female adults with moderate to severe GL, LCL, and FHL at maximum contraction as assessed by investigators using the AGLSS, LCLSS, and FHLSS, respectively. To avoid confounding the study results, washout from prior facial aesthetic treatments is required as described in the eligibility criteria.

Selection of Doses in the Study

BOTOX Cosmetic is currently approved for aesthetic treatment of GL, LCL and FHL. The total dose, dilution, injection pattern, and route of administration will follow the approved label, and each eligible subject will receive a fixed dose of 64 U of BOTOX Cosmetic on Day 1 (20 U to the glabellar complex, 24 U to the lateral canthal areas, and 20 U to the frontalis muscles).

5 STUDY ACTIVITIES

5.1 Eligibility Criteria

Subjects must meet all of the following criteria in order to be included in the study. Anything other than a positive response to the questions below will result in exclusion from study participation.

Rescreening is not allowed for individuals who do not meet Eligibility Criterion #8 (listed below). Any attempt to rescreen a subject must only occur after agreement with the sponsor. Rescreening can only occur once for any given potential subject.

Consent

1. Subjects must voluntarily sign and date an informed consent, approved by an independent ethics committee (IEC)/institutional review board (IRB), prior to the initiation of any screening or study-specific procedures.
2. Subjects are willing and able to comply with procedures required in this protocol.
3. Subjects must agree to have photos and videos taken during study visits. Subjects must consent to having photographs and videos taken for research/educational purposes but may still participate if he/she declines use of the photographs and videos for other purposes.

Demographic and Subject Characteristics

4. Adult male or female, at least 18 years old, at the time of signing the informed consent.
5. Subjects must have sufficient visual acuity without the use of eyeglasses (contact lens use acceptable) to accurately assess their facial wrinkles.
6. Subject must be able to follow study instructions and complete study assessment tools without any assistance or alterations to the assessment tools and complete all required study procedures.
7. Subject must be in good health as determined by medical history, vital signs, and investigator's judgement, including no known active pandemic infection.

[figure not shown]
Condition

8. Subject meets all of the following criteria prior to dosing on Day 1, as determined by the investigator:
 - GL of Moderate (Grade 2) to Severe (Grade 3) on AGLSS at maximum contraction.

- LCL of Moderate (Grade 2) to Severe (Grade 3) bilaterally (severity identical on both sides) on LCLSS at maximum contraction.
- FHL of Moderate (Grade 2) to Severe (Grade 3) on FHLSS at maximum contraction.

Subject History

[figure not shown]
9. No history of known immunization or hypersensitivity to any botulinum toxin serotype.
10. No history of an allergic reaction or significant sensitivity to constituents of the study drug (and its excipients) and/or other products in the same class.
11. No history of clinically significant (per investigator's judgment) drug or alcohol abuse within the last 6 months.
12. No presence of tattoos, jewelry, or clothing which obscures or interferes with the target area of interest and cannot be removed.

14. No history of clinically significant medical conditions or presence of current uncontrolled systemic disease or any other reasons, in the investigator's opinion, that may put the subject at significant risk, may confound the study results, or may interfere significantly with participation in the study.
15. Subjects cannot be directly or indirectly involved in the conduct and administration of this study as a principal investigator, sub-investigator, study coordinator, or other study staff member; or employee of the sponsor, or a first-degree family member, significant other, or relative residing with one of the above persons involved directly or indirectly in the study.
16. No known active severe acute respiratory syndrome coronavirus 2 (SARS-CoV-2) infection. If a subject has signs/symptoms suggestive of SARS-CoV-2 infection, the subject must have a negative molecular (e.g., polymerase chain reaction [PCR] test result). Note: SARS-CoV-2 diagnostic tests should be applied following local requirements/recommendations.

17. Subjects who do not meet SARS-CoV-2 infection eligibility criteria must be screen failed and may only rescreen after they meet the following SARS-CoV-2 infection viral clearance criteria:

- At least 10 days since first positive test result have passed in asymptomatic subjects or at least 10 days since recovery, defined as resolution of fever without use of antipyretics and improvement in symptoms

20. No history of any botulinum neurotoxin of any serotype for any indication within 6 months prior to Day 1.

21. No clinically significant abnormal vital signs at Day 1.

Contraception

22. Female subjects of childbearing potential must have a negative urine pregnancy test at Day 1 prior to study treatment.

23. Female subjects of childbearing potential must practice at least 1 protocol-specified method of birth control that is effective from study drug administration (Day 1) through a minimum of 60 days or until last study follow-up visit, whichever is longer. Female subjects of nonchildbearing potential do not need to use birth control.

24. Female subject who is not pregnant or breastfeeding and is not considering becoming pregnant or donating eggs from study drug administration (Day 1) through a minimum of 60 days after study drug administration or until last study follow-up visit, whichever is longer.

Concomitant Medications or Procedures

25. No anticipated need for treatment with botulinum toxin of any serotype for any indication during the study (other than study drug).

26. No anticipated need for surgery or overnight hospitalization during the study.

27. No plans for an extended absence away from the immediate area of the study site that would preclude them from returning for all protocol-specified study visits.
28. In the investigator's opinion, subject is able and willing to maintain his or her standardized skin care regimen throughout the study period.
29. Subject must not have been treated with any investigational drug within 30 days or 5 half-lives of the drug (whichever is longer) prior to the first dose of study drug or is currently enrolled in another clinical study or was previously enrolled in this study.

5.2 Contraception Recommendations

Contraception Requirements for Females

Subjects must follow the following contraceptive guidelines as specified:

- **Females, Non-Childbearing Potential**

Females do not need to use birth control during or following study drug treatment if considered of non-childbearing potential due to meeting any of the following criteria:

1. Premenopausal female with permanent sterility or permanent infertility due to one of the following:
 - Permanent sterility due to a hysterectomy, bilateral salpingectomy, bilateral oophorectomy.
 - Non-surgical permanent infertility due to Mullerian agenesis, androgen insensitivity, or gonadal dysgenesis; investigator discretion should be applied to determining study entry for these individuals.
2. Postmenopausal female
 - A postmenopausal state is defined as no menses for 12 months without an alternative medical cause.
 - A high follicle stimulating hormone (FSH) level in the postmenopausal range may be used to confirm a postmenopausal state in women not using hormonal contraception or hormone replacement therapy. However, in the absence of 12 months of amenorrhea, confirmation with more than 1 FSH measurement is required.
 - Females on hormone replacement therapy and whose menopausal status is in doubt, as determined by the investigator, will be required to use one of the non-hormonal (highly) effective contraception methods if they wish to continue their hormone replacement therapy during the study. Otherwise, they must discontinue hormone replacement therapy to allow confirmation of postmenopausal status before study enrollment.

[figure not shown]
- Females, of Childbearing Potential
 - Females of childbearing potential must avoid pregnancy from study drug administration (Day 1) through a minimum of 60 days after the last dose or until last study follow-up visit, whichever is longer.
 - Females must commit to one of the following methods of birth control:
 - Combined (estrogen and progestogen containing) hormonal birth control (oral, intravaginal, transdermal, injectable) associated with inhibition of ovulation-initiated at least 30 days prior to Day 1.
 - Progestogen-only hormonal birth control (oral, injectable, implantable) associated with inhibition of ovulation initiated at least 30 days prior to Day 1.
 - Bilateral tubal occlusion/ligation (can be via hysteroscopy, provided a hysterosalpingogram confirms success of the procedure).
 - Intrauterine device (IUD).
 - Intrauterine hormone-releasing system.
 - Vasectomized partner (provided the partner has received medical confirmation of the surgical success of the vasectomy and is the sole sexual partner of the trial subject).
 - Practice true abstinence, defined as: Refraining from heterosexual intercourse when this is in line with the preferred and usual lifestyle of the subject (periodic abstinence [e.g., calendar, ovulation, symptothermal, post-ovulation methods] and withdrawal are not acceptable).
 - Progestogen-only oral hormonal contraception, where inhibition of ovulation is not the primary mode of action, initiated at least 30 days prior to Day 1.
 - Male or female condom with or without spermicide.
 - Cap, diaphragm, or sponge with spermicide.
 - A combination of male condom with cap, diaphragm, or sponge with spermicide (double barrier method).

Contraception recommendations related to use of concomitant therapies prescribed should be based on the local label.

5.3 Prohibited Medications and Procedures

The decision to administer a prohibited medication/treatment during the study period is done with the safety of the subject as the primary consideration. When possible, the sponsor is to be notified before the prohibited medication/treatment is administered.

In addition to the medications listed in the eligibility criteria, no other facial cosmetic procedures or treatments are to be performed throughout the duration of the study. Prohibited treatments and procedures include, but are not limited to:

All other investigational drugs are prohibited.

5.4 Prior and Concomitant Procedures

Any medication or vaccine (including over-the-counter or prescription medicines, vitamins, and/or herbal supplements) that the subject is receiving at the time of enrollment or receives during the study must be recorded from 30 days prior to the study drug administration through the study exit. See below for details on special handling for the COVID-19 vaccine.

The use of any medication during the study (including prescription or over-the-counter medication, vitamins, and/or herbal supplements) is to be recorded on the subject's electronic case report form (eCRF) at each visit along with the reason the medication is taken, dates of use, and dosing regimen. Concomitant medications and concurrent procedures will also be collected at each visit.

Study site personnel should notify the sponsor immediately if a subject uses a concomitant medication or has a concurrent procedure that is prohibited per protocol (see Section 5.3). Subjects who use prohibited concomitant medications or have a prohibited concurrent procedure may be discontinued at the discretion of the investigator or sponsor. Concomitant medications and concurrent procedures will be tabulated and listed.

Non-live vaccines may be used during the study, if not contraindicated or medically inappropriate. When possible, study drug should be given at least \pm 7 days from vaccine administration.

Co-administration of aminoglycosides or agents that could interfere with neuromuscular transmission (e.g., curare-like agents) or muscle relaxants are to be used with caution as the effects of the toxin, theoretically, could be potentiated.

Systemic and topical hormones and their derivatives (e.g., sex steroids - androgens, estrogens, progesterone) should be maintained throughout the study period to avoid changes in skin, including but not limited to:

- Oral birth control
- IUDs/implants/injections
- Oral supplements including testosterone & estrogens and their derivatives, dehydroepiandrosterone (DHEA), etc.
- Topicals (anywhere on the body) including testosterone & estrogens and their derivatives, DHEA, etc.
- Androgel, Axiron, Testim, Fortesta, Vogelxo
- Emedelle (methyl estradiolpropanoate), Rejuvenate, All Natural Bioidentical Estradiol, Emerita Phytoestrogen

Subjects should maintain their skin care regimen throughout the study period.

Any questions regarding concomitant or prior procedures should be raised to the AbbVie non-emergency contact. Information regarding potential drug interactions with BOTOX Cosmetic can be located in the BOTOX Cosmetic Investigator's Brochure.

Subjects must be able to safely discontinue any prohibited medications as described in the eligibility criteria. Subjects must consent to the study prior to discontinuing any prohibited medications for the purpose of meeting study eligibility.

COVID-19 Pandemic-Related Vaccination Guidance

Select non-live vaccines (e.g., messenger ribonucleic acid, non-replicating viral vector, protein subunit, etc.) to prevent SARS-CoV-2 infection may be administered during the study, as long as components of the vaccine are not contraindicated.

The decision to receive a locally available vaccine should be based on local guidance and an individual discussion between the treating physician and the subject.

The potential impact of BOTOX Cosmetic on SARS-CoV-2 vaccination is unknown. Therefore, study drug should be administered as follows:

- Study drug is preferred to be administered, when possible, at least \pm 14 days from the SARS-CoV-2 vaccine administration.

Note: The above guidance applies to all SARS-CoV-2 vaccine doses given as part of the complete vaccination course.

These recommendations may be subject to change based on the evolving knowledge around the use of SARS-CoV-2 vaccines and as more data are collected in real-world scenarios and clinical trials.

Any SARS-CoV-2 vaccine information must be documented on the COVID-19 vaccine eCRF. Refer to the Operations Manual for instructions on reporting any AEs associated with the COVID-19 vaccine.

5.5 Withdrawal of Subjects and Discontinuation of Study

A subject may voluntarily withdraw or be withdrawn from the study at any time for reasons including, but not limited to, the following:

- The investigator believes it is in the best interest of the subject.
- The subject requests withdrawal from the study.
- Subject is significantly noncompliant with study procedures.

This is a single treatment study. Treatment will be administered on Day 1 only. In case of pregnancy or AE during the study after study treatment is provided, the subject should continue in the study for safety follow-up.

In case the subject has a desire to end his/her participation, or is discontinued for any reason, the Early Exit Visit procedures should be completed.

For subjects to be considered lost to follow-up, reasonable attempts must be made to obtain information on the subject's final status. At a minimum, 2 telephone calls must be made and 1 certified letter must be sent and documented in the subject's source documentation.

AbbVie may terminate this study prematurely, either in its entirety or at any site. The investigator may also stop the study at his/her site if he/she has safety concerns. If AbbVie terminates the study for safety reasons, AbbVie will promptly notify the investigator.

COVID-19 Pandemic-Related Acceptable Protocol Modification

During the COVID-19 pandemic, it has been necessary to employ mitigation strategies to enable the investigator to ensure subject safety and continuity of care. Acceptable mitigation strategies are identified and included in the Operations Manual ([Appendix E](#)).

The investigator should contact the sponsor's non-emergency medical contact before discontinuing a subject from the study for a reason other than described in the protocol to ensure all acceptable mitigation steps have been explored.

5.6 Follow-Up After Subject Discontinuation of Study Drug or from Study

To minimize missing data for efficacy and safety assessments, subjects should continue to be followed for all regularly scheduled visits, unless subjects have decided to discontinue the study participation entirely (withdrawal of informed consent). Subjects should be advised on the continued scientific importance of their data.

If a subject prematurely discontinues study participation (withdrawal of informed consent), the procedures outlined for the Early Exit visit should be completed as soon as possible, preferably within 2 weeks. In addition, if subject is willing, a 30-day follow-up phone call after the last dose of study drug may be completed to ensure all treatment-emergent adverse events (TEAEs)/serious adverse events (SAEs) have been resolved.

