1 SYNOPSIS

Title: A Prospective, Multi-center, Open-label Study to Evaluate Subject Satisfaction and Natural Outcomes Following Administration of BOTOX® Cosmetic (Botulinum Toxin Type A) Purified Neurotoxin Complex in Subjects with Upper Facial Lines (Glabellar Lines, Lateral Canthal Lines, and Forehead Lines)

| | |
|--|---|
| Background and Rationale: | BOTOX Cosmetic is an acetylcholine release inhibitor and a neuromuscular blocking agent approved for aesthetic treatment of glabellar lines (GL), lateral canthal lines (LCL), and forehead lines (FHL). It is typical for some clinicians to administer lower than labeled doses of botulinum toxin to avoid a "frozen" look. The intent of this study is to evaluate subject satisfaction and natural outcomes following administration of 64 Units (U) of BOTOX Cosmetic for multiple upper facial areas (GL, LCL, and FHL). |
| Objective and Primary Endpoint: | The objective of this study is to evaluate subject satisfaction and natural outcomes following simultaneous treatment of multiple upper facial lines (GL, LCL, and FHL) with 64 U of BOTOX Cosmetic. The primary endpoint is the responder status of Mostly satisfied or Very satisfied on the Facial Line Satisfaction Questionnaire (FLSQ) Follow-up Item 4 at Day 30. |
| Investigators: | Multi-center |
| Study Sites: | Approximately 10 sites |
| Study Population and Number of Subjects to be Enrolled: | Approximately 100 subjects in general good health with moderate to severe GL, LCL, and FHL. |
| Investigational Plan: | This is a prospective, multicenter, open-label study. Eligible subjects will receive a single fixed dose of 64 U of BOTOX Cosmetic on Day 1. Subjects will be followed monthly for up to 180 days after treatment. |
| Key Eligibility Criteria: | Adult male or female; ≥ 18 years of age; moderate to severe GL, LCL, and FHL, as determined by the investigator at maximum contraction at Day 1 |
| Study Drug and Duration of Treatment: | Single treatment of BOTOX Cosmetic (64 U) |
| Date of Protocol Synopsis: | 14 December 2023 |

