2.2 Benefits and Risks to Subjects

The clinical efficacy and safety profile of BOTOX Cosmetic has been demonstrated in multiple clinical trials across several indications, with favorable benefit risk profiles. In general, adverse reactions occur within the first few days to weeks following injection of BOTOX Cosmetic and, while generally transient, may have a duration of several months or, in rare cases, longer.

While Allergan (an AbbVie company) does not consider Coronavirus disease 2019 (COVID-19) to be a safety concern for BOTOX Cosmetic due to its mechanism of action and route of administration, the sponsor is monitoring COVID-19 events during the pandemic closely. A review of COVID-19 events for the period of 01 January 2019 through 31 December 2021 did not identify any new or significant safety findings for the subjects receiving BOTOX Cosmetic treatment. Overall, the clinical course and presentation of patients with COVID-19 infection coincident with BOTOX Cosmetic is consistent with what has been described for the general population. Considering the COVID-19 pandemic and based on the limited information to date, no additional risk to study participants is anticipated with the use of BOTOX Cosmetic.

For further details, please see findings from completed studies, including safety data in the current BOTOX Cosmetic investigator's brochure.

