5.7 Study Drug

Study drugs refer to drugs that are used (or can be used) in this study to assess the safety and the efficacy of the Investigational Product. Investigators will assess the relationship of adverse events to the use of study drugs.

Study drug will be provided by AbbVie and administered on Day 1, and subjects will not be retreated ([Table 1](#)).

Table 1. Study Drug Information

| Product | Mode of Administration | Formulation | Total Treatment Dose | Manufacturer |
|-----------------------------|-------------------------|---------------------|----------------------|--------------|
| BOTOX Cosmetic (100 U/vial) | Intramuscular Injection | Powder for solution | 64 U | Allergan |

Study drug provided by AbbVie should not be substituted or alternately sourced unless otherwise directed by AbbVie. Upon receipt, study drug should be stored as specified on the package insert and kept in a secure location. Study drug will only be used for the conduct of this study.

Additional information regarding the study drug and administration is available in the Operations Manual ([Appendix E](#)).

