Such an event can result from use of the drug as stipulated in the protocol or labeling, as well as from "special situations" such as accidental or intentional overdose, medication error, occupational or accidental exposure, off-label use, drug abuse, drug misuse, or drug withdrawal, all which must be reported whether associated with an AE or not. Any worsening of a pre-existing condition or illness is considered an AE. Worsening in severity of a reported AE should be reported as a new AE. Laboratory abnormalities and changes in vital signs are considered to be AEs only if they result in discontinuation from the study, necessitate therapeutic medical intervention, and/or if the investigator considers them to be AEs.

The investigators will monitor each subject for clinical and laboratory evidence of AEs on a routine basis throughout the study. All AEs will be followed to a satisfactory conclusion.

An elective surgery/procedure scheduled to occur during a study will not be considered an AE if the surgery/procedure is being performed for a pre-existing condition and/or the surgery/procedure has been pre-planned prior to study entry. However, if the pre-existing condition deteriorates unexpectedly during the study (e.g., surgery performed earlier than planned), then the deterioration of the condition for which the elective surgery/procedure is being done will be considered an AE.

If an AE, whether associated with study drug or not, meets any of the following criteria, it is to be reported to AbbVie clinical pharmacovigilance as a SAE within 24 hours of the site being made aware of the SAE (refer to Section 4.2 of the Operations Manual for reporting details and contact information):

| | |
|---|--|
| Death of Subject | An event that results in the death of a subject. |
| Life-Threatening | An event that, in the opinion of the investigator, would have resulted in immediate fatality if medical intervention had not been taken. This does not include an event that would have been fatal if it had occurred in a more severe form. |
| Hospitalization or Prolongation of Hospitalization | An event that results in an admission to the hospital for any length of time or prolongs the subject's hospital stay. This does not include an emergency room visit or admission to an outpatient facility. |
| Congenital Anomaly | An anomaly detected at or after birth, or any anomaly that results in fetal loss. |

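### The optional phone call meant to confirm that adverse events have resolved after withdrawal is timed from the Day 1 dose, so its date has passed for most possible withdrawal days and may be too early for the rest (minor)

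*Protocol*

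**What the plan says.** Protocol 5.6 describes two contacts for a subject who leaves the study by withdrawing consent. The first is the Early Exit visit, to be done promptly and ideally inside two weeks. The second comes on top of it and depends on the subject's willingness: "a 30-day follow-up phone call after the last dose of study drug may be completed to ensure all treatment-emergent adverse events" and serious adverse events have been resolved.

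The date of the last dose is the same for everyone. Section 5.5 states: "This is a single treatment study. Treatment will be administered on Day 1 only". Section 5.7 says study drug is "administered on Day 1, and subjects will not be retreated". The Synopsis sets the length of observation: "Subjects will be followed monthly for up to 180 days after treatment". Section 5.5 allows withdrawal at any point.

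Three other statements bear on the call:

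- Section 2.2 places the onset of reactions in the first days to weeks, and says they "while generally transient, may have a duration of several months or, in rare cases, longer".
- Section 6.1 says: "All AEs will be followed to a satisfactory conclusion".
- Section 6.1 also sets the collection period for adverse events as the longer of 30 days and the time to the last follow-up visit. After that, only serious events that are reported spontaneously are collected.

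**The concern.** A call 30 days after the last dose works as a closing contact when the last dose is near the time the subject leaves. In a single-dose study with six months of follow-up, the two dates can be months apart. The call is there to confirm that events have resolved, yet for most of the follow-up period its date comes before the withdrawal it is meant to follow.

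At stake are the outcome and end date of events still open when a subject leaves. SAP 10.2.3 summarises the duration of treatment-related events and of possible distant spread of toxin events, and by default takes the duration of an ongoing event as its duration at study exit. For a subject who exits early with such an event, the recorded duration is therefore cut off at exit. Without a workable later contact, nothing in the described procedure would replace it. The primary and secondary endpoints are not affected.

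**Working it through.** The plan gives no figure of its own here, so there is none to reproduce. The check is day arithmetic plus a comparison of sections.

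**Inputs**
- Dose day: Day 1, no retreatment (Protocol 5.5, 5.7).
- Call: 30 days after the last dose, optional (5.6).
- Study exit: Day 180 (4.1).
- Early Exit visit: ideally within 14 days of withdrawal (5.6).

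**Step 1. Date of the call.** 1 + 30 = Day 31. If Day 1 is counted as the first of the 30 days, it is Day 30.

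**Step 2. Share of possible withdrawal days after the call date.**
- Days 2 to 180: 180 − 2 + 1 = 179 days.
- Days 32 to 180: 180 − 32 + 1 = 149 days.
- 149 / 179 = 83.2%. With the call on Day 30, it is 150 / 179 = 83.8%.

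This counts calendar days. It equals a share of withdrawals only if withdrawal is equally likely on every day, which the documents neither say nor allow one to check.

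**Step 3. Examples.**

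| Withdrawal day | Early Exit window | Call date (Day 31) relative to withdrawal |
|---|---|---|
| 10 | 10 to 24 | 21 days after |
| 20 | 20 to 34 | 11 days after |
| 60 | 60 to 74 | 29 days before |
| 90 | 90 to 104 | 59 days before |
| 120 | 120 to 134 | 89 days before |
| 150 | 150 to 164 | 119 days before |

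For withdrawals from Day 18 on (18 + 14 = 32), the Early Exit visit itself may fall after the call date.

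**Step 4. Purpose against timing.** For a withdrawal after Day 31 the call, read literally, cannot follow the withdrawal. For a withdrawal before Day 31 it can, but it takes place 30 days after the injection. Section 2.2 allows reactions to last several months, so a call on Day 31 may find such an event still open. Section 5.6 describes no later contact.

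**Step 5. Comparison within Section 6.1.** Day 31 matches the 30-day minimum for adverse event collection. It does not match the statement that all events are followed to a conclusion, which has no end date and, in the text available, no contact schedule for subjects who have left.

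**The case against.** There is a good case that the call does what it was designed to do. Section 6.1 sets a 30-day floor for adverse event collection. A subject whose Early Exit visit falls before about Day 31 would miss that floor, and the call closes the gap. For later withdrawals the Early Exit visit is already past the floor, so no call is needed for that purpose. This stands as a rationale for the timing. It does not rescue the stated purpose, which is confirming resolution rather than completing a collection window.

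The affected group is also narrow. Section 5.5 says subjects with an adverse event or a pregnancy should stay in the study for safety follow-up, and Section 5.6 keeps discontinued subjects on the regular visit schedule unless they withdraw consent entirely. Those who do withdraw can be contacted only as far as they agree. Section 2.2 describes reactions as usually transient and early in onset, so open reactions at late withdrawals are probably uncommon. All of this stands.

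Three stronger readings are tempting, and the documents do not support them:

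- A reader might infer that the call is the only safety contact after withdrawal. It is not. Sections 5.5 and 5.6 both require Early Exit procedures, and the Section 6.1 duty to follow events continues.
- A reader might take 83% as the share of withdrawing subjects, or of open events, that go without follow-up. It is a share of calendar days.
- A reader might set the call against Section 5.2, under which women of childbearing potential "must avoid pregnancy from study drug administration (Day 1) through a minimum of 60 days after the last dose" or until the last follow-up visit, if that is later, and conclude that pregnancies will be missed. But Section 5.6 limits the call to adverse events, the 60 days is an avoidance period and not a contact schedule, and Section 6.1 has its own rule for pregnancy reporting.

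Finally, the schedule tables and the Operations Manual are not in the public text and may describe further follow-up. They could add a contact, but they would not change the anchor written in Section 5.6.

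**Conclusion.** The point holds in a narrow form. Beyond the Early Exit visit, the one contact that Section 5.6 describes for a subject who withdraws consent is optional and tied to Day 1. It is already past on 149 of the 179 possible withdrawal days. On the others it may come too soon to confirm resolution of a long reaction. The weakness concerns resolution rather than onset, since onset is expected early.

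The date arithmetic is certain to within one day, depending on how Day 1 is counted. How many subjects are affected is unknown, because the documents give neither a withdrawal rate nor a rate of events open at exit; the number is probably small. The conclusion assumes that Section 5.6 is read literally and that the unseen operational documents do not already supply a later contact. Severity: minor.

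**What to change.** Reconcile Section 5.6 with Sections 2.2, 5.5 and 6.1. The contact meant to confirm resolution of events open at exit should be able to take place after withdrawal, if the subject agrees, and should record each event's outcome and end date. If the call is instead meant only to complete the 30-day collection minimum, Section 5.6 should say so, and the protocol should state how the follow-up duty in Section 6.1 is met for subjects who have left. The choice of anchor and interval belongs to the sponsor.

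The cost is about one sentence in the protocol or a clarification letter, with a matching date field in the case report form. The plan already allows the call, and it concerns only subjects who exit early. Some of them will decline or not be reached, so some end dates will still be missing.
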